11.2 Analysis of Secondary Endpoints

11.2.1 Secondary Endpoints and Hypothesis Testing

Once the null hypothesis of the primary endpoint has been rejected, the secondary endpoints below will be tested using a fixed sequence testing procedure, in order to maintain the overall two-sided type I error of 0.05. If the claim of superiority or non-inferiority is successful and the test will progress to the next comparison in sequence as follows.

Table 6 Key Secondary Endpoints Fixed Sequence Testing Procedure

Test	Variable	Comparison
1	Proportion of subjects with mean hemoglobin level during the evaluation period defined as Week 28 until Week 52 \geq 10.0 g/dL (U.S.) or Proportion of Hb responders in the average of weeks 28 to 36 within the target range of 10.0 to 12.0 g/dL without having received rescue therapy. (Ex-U.S.).	Non-inferiority of roxadustat versus EPO with margin of -0.15
2	LDL cholesterol change from BL to the average of weeks 12 to 28.	Superiority of roxadustat versus EPO
3	Hemoglobin change from baseline to the average level during Weeks 18 to 24 for subjects with baseline hsCRP > ULN	Non-inferiority of roxadustat versus EPO
4	Average monthly IV iron (mg) use per subject during weeks 28 to 52.	Superiority of roxadustat versus EPO
5	Time to first RBC Transfusion during the treatment.	Non-inferiority of roxadustat versus Epo with margin of 1.8
6	MAP change from BL to the average MAP of weeks 20 to 28.	Superiority of roxadustat versus EPO
7	Time to first exacerbation of hypertension: An increase from baseline of \geq 20 mmHg systolic blood pressure (SBP) and SBP \geq 170 mmHg or an increase from baseline of \geq 15 mmHg diastolic blood pressure (DBP) and DBP \geq 100 mmHg during Weeks 28 to 52.	Superiority and Non-inferiority of roxadustat versus EPO with margin of 1.8

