##### 3.2.2 Secondary Efficacy Endpoints

The secondary efficacy endpoints in this study are:

- US (FDA) submission: Proportion of subjects with mean Hb level during the evaluation period defined as Week 28 until Week 52  $\geq 10.0$  g/dL.
- EU regulatory submission: Hemoglobin (Hb) response, defined as mean Hb during Weeks 28 to 36 within the target range of 10.0 to 12.0 g/dL without having received rescue therapy within 6 weeks prior to and during this 8-week evaluation period.
- Average monthly IV iron use per subject during Weeks 1 to 36 (monthly defined as a period of 4 weeks).
- Change from BL in low-density lipoprotein (LDL) cholesterol to the average LDL cholesterol of Weeks 12 to 28
- Change from BL in SF-36 Physical Functioning (PF) subscore to the average PF subscore of Weeks 12 to 28
- Change from BL in SF-36 Vitality (VT) subscore to the average VT subscore of Weeks 12 to 28
- Effect on predialysis BP:
  - Time to an exacerbation of hypertension from BL during Weeks 1 to 36

- An increase from BL of  $\geq 20$  mm Hg systolic blood pressure (sBP) and sBP  $> 170$  mmHg

OR

- An increase from BL of  $\geq 15$  mm Hg diastolic blood pressure (dBP) and dBP  $> 100$  mmHg
- Change from BL in mean arterial pressure (MAP) to the MAP value averaged over Weeks 20 to 28

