#### 9.4.3.2 Secondary Efficacy Analyses

Once the primary hypothesis is rejected for the primary endpoint, the secondary variables will be tested using a fixed sequence testing procedure as follows:

- For US (FDA) submission: Proportion of subjects with mean Hb level during the evaluation period defined as Week 28 until Week 52  $\geq 10.0$  g/dL.
- EU regulatory submission: Hemoglobin (Hb) response, defined as mean Hb during Weeks 28 to 36 within the range of 10.0 to 12.0 g/dL without having received rescue therapy within 6 weeks prior to and during this 8-week evaluation period.

The hypothesis to be tested for the first secondary efficacy analysis is:

H0: Hb response rate for subjects in the roxadustat group - Hb responder rate for subjects in the epoetin alfa group  $\leq -15\%$

Versus

H1: Hb response rate for subjects in the roxadustat group - Hb responder rate for subjects in the epoetin alfa group  $> -15\%$ .

A 2-sided 95% CI for the difference of two responder rates (roxadustat-ESA) based on the Miettinen and Nurminen approach adjusting for treatment group and other stratification factors will be calculated and H0 will be rejected if the lower bound of the 95% CI is greater than  $-15\%$ .

- The average monthly iron use during Weeks 1 to 36 will be compared between the 2 treatment groups using an ANCOVA model with BL iron replete as a covariate, and treatment arm and randomization stratification factors as fixed effects. Superiority will be declared if the lower bound of the 2-sided 95% CI of the difference between epoetin alfa and roxadustat exceeds 0.
- The change in low-density lipoprotein (LDL) cholesterol averaged over Weeks 12 to 28 from BL will be analyzed using an MMRM model with BL LDL cholesterol as a covariate and treatment arm, visit, interaction of treatment arm and visit, and randomization stratification factors as fixed effects. Superiority will be declared if the lower bound of the 2-sided 95% CI of the difference between epoetin alfa and roxadustat exceeds 0.
- Time to exacerbation of BP will be analyzed using the Cox Proportional Hazards model adjusting for treatment arm and randomization stratification factors. Superiority of roxadustat vs. epoetin alfa will be declared if the upper bound of the 2-sided 95% CI of the hazard ratio is  $< 1$ .

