4.2 Secondary Efficacy Endpoints

The secondary efficacy endpoints in this study are as below for both US and Ex-US submission unless otherwise specified:

- US (FDA) submission: Proportion of subjects with mean hemoglobin level during the evaluation period defined as Week 28 until Week 52 ≥ 10.0 g/dL.
- Ex-US submission: Proportion of subjects with hemoglobin response, defined as mean hemoglobin during Weeks 28 to 36 within the target range of 10.0 to 12.0 g/dL without having received rescue therapy within 6 weeks prior to and during this 8-week evaluation period.
- Change from baseline in Low Density Lipoprotein (LDL) cholesterol to the average LDL cholesterol of weeks 12 to 28.
- Hemoglobin change from baseline to the average level during the Weeks 18 to 24 for subjects with baseline hs-CRP $>$ ULN.
- Average monthly IV iron use per subject during the Treatment Period during Weeks 28 to 52 (monthly defined as a period of 4 weeks).
- Time to first RBC Transfusion during the treatment
- Change from BL in mean arterial pressure (MAP) to the MAP value averaged over weeks 20 to 28
- Time to first exacerbation of hypertension: An increase from BL of ≥ 20 mm systolic blood pressure (SBP) and SBP ≥ 170 mmHg or an increase from baseline of ≥ 15 mmHg diastolic blood pressure (DBP) and DBP ≥ 100 mmHg during Weeks 28 to 52.

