4.3 Additional Evaluation of Efficacy

The additional efficacy evaluations in this study are:

- **Hemoglobin Maintenance:**
 - Hemoglobin long-term Maintenance: Mean change from baseline in hemoglobin averaged over 8 weeks of treatment at Weeks 44-52 without

- rescue therapy within 6 weeks prior to and during this 8-week evaluation period.
- Mean change from baseline in hemoglobin averaged over the Week 96 to 104 of treatment, without rescue therapy within 6 weeks prior to and during this 8-week evaluation period.
 - Change from baseline in hemoglobin at each of the selected post-dosing time points.
 - Proportion of subjects with Hb ≥ 10 g/dL averaged over Weeks 28 to 36, 44 to 52, and 96 to 104 of treatment without rescue therapy within 6 weeks prior to and during the evaluation periods.
 - Proportion of subjects with Hb ≥ 10 g/dL averaged over Weeks 28 to 36, 44 to 52, and 96 to 104 of treatment regardless of rescue therapy
 - Proportion of subjects with Hb within 10-12 g/dL averaged over Weeks 28 to 36, 44 to 52, and 96 to 104 of treatment without rescue therapy within 6 weeks prior to and during these 8-week evaluation periods.
 - Proportion of subjects with Hb within 10-12 g/dL averaged over Weeks 28 to 36, 44 to 52, and 96 to 104 of treatment regardless of rescue therapy use.
 - Hemoglobin change from baseline to the average hemoglobin value of weeks 28 to 36, 44 to 52, and 96 to 104 of treatment regardless of the use of rescue therapy.
- **Iron Supplement:**
 - Time to and Proportion of subjects who has requirement for IV iron supplementation.
 - Mean monthly IV iron (mg) per subject during weeks 28-52, 53-104, and 105 -EOT.
 - Mean monthly oral iron (mg) use per subject during 28-52, 53-104, and 105 - EOT.
 - Proportion of subjects who has Requirement for only oral iron supplementation (Week 1 to 52).
 - **Hospitalizations**
 - Time to first hospitalization (% of subjects) up to Week 52, 7 days after Last Dose. Time to first hospitalization or skilled nursing facility (% of subjects) up to Week 52, 7 days after Last Dose.
 - Number of days of hospitalizations due to AE per subject-exposure year (PEY)
 - Number of days in hospital or skilled nursing facility due to AE per patient-year exposure (PEY)
 - Number of days in medical-facility (hospital, skilled nursing facility, emergency room, or overnight observation) due to AE per patient-year exposure (PEY)

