Change from baseline in Hemoglobin from baseline to the average level during the Week 18 to 24 will be analyzed using the ANCOVA MI as the primary endpoints. Both Non-inferiority of roxadustat vs. Epoetin and superiority will be tested. The non-inferiority margin is fixed as a difference of -0.75.

11.2.2.4 Average Monthly of IV Iron Use during Weeks 28 to 52.

The average monthly IV iron use during Weeks 28 to 52 Treatment Period will be calculated for monthly intervals. The Treatment Period will be divided in periods of 28 days and for each of these periods the monthly mean of IV iron will be calculated using the following formula:

Monthly iron use for each subject = Total IV iron in mg / [(last visit date – first dose date of study medication +1)/ 28]

The average monthly iron use will be compared between the 2 treatment groups using An ANCOVA model with baseline iron repletion status, treatment group, and stratification factors as fixed effects. Superiority will be declared if the lower bound of the 2-sided 95% confidence interval of the difference between active control and roxadustat exceeds 0.

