11.3.3.3 Use of Iron

IV Iron

Only IV iron therapy that started during the study treatment and up to the ET/EOT Visit will be taken into account for the total amount.

The average monthly IV iron use during weeks 53 to EOS will be calculated for monthly intervals. The Treatment Period will be divided in periods of 28 days and for each of these periods the monthly mean of IV iron will be used using the following formula:

Monthly iron use for each subject = $\text{Total IV iron in mg} / [(\text{last visit date} - \text{first dose date of study medication in the period} + 1) / 28]$

The following 2 endpoints will be analyzed:

- Proportion of subjects who receive IV iron. The proportion of subjects who received IV iron will be compared between the 2 treatments using logistic regression model adjusting for baseline iron repletion status and treatment group and stratification factors as fixed effects. (This will be performed for week 1 to week 36 as well).
- The average monthly iron use will be compared between the 2 treatment groups using ANCOVA model with baseline iron repletion status, and treatment group, and stratification factors as fixed effects.

Oral iron

The average monthly oral iron use during Weeks 28 to 52, and weeks 53 to ET/EOT will be calculated similarly to IV iron for monthly intervals.

The following 2 endpoints will be analyzed:

- Proportion of subjects who receive Oral iron. The proportion of subjects who received oral iron will be compared between the 2 treatment groups using logistic regression model adjusting for baseline iron repletion status, treatment group and stratification factors as fixed effects.
- The average monthly oral iron use will be compared between the 2 treatment groups using ANCOVA model with baseline iron repletion status, treatment group, and stratification factors as fixed effects.

In addition the proportion of subjects who received both IV and/or oral iron will be compared between the 2 treatments using logistic regression model adjusting for baseline iron repletion status and treatment group and stratification factors as fixed effects.

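### The SAP tests IV iron over Weeks 28-52 instead of the protocol's Weeks 1-36 without flagging the change, and its printed formula does not compute a Weeks 28-52 average

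*SAP*

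**What the plan says.** **Protocol.** Section 3.2.2 lists "Average monthly IV iron use per subject during Weeks 1 to 36 (monthly defined as a period of 4 weeks" as a secondary endpoint, as does the synopsis. Section 9.4.3.2 puts it in the fixed sequence: "The average monthly iron use during Weeks 1 to 36 will be compared between the 2 treatment groups using an ANCOVA model". Section 9.6 commits the SAP to drawing attention to any significant departure from the protocol analyses.

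**SAP.** Section 1 presents the document as a fuller technical account of protocol Amendment 2. Section 4.2 nevertheless defines the endpoint as "Average monthly IV iron use per subject during the Treatment Period during Weeks 28 to 52", and Table 6 makes it Test 4: "Average monthly IV iron (mg) use per subject during weeks 28 to 52". The additional endpoints in 4.3 are "Mean monthly IV iron (mg) per subject during weeks 28-52, 53-104, and 105 -EOT". For the protocol's window, 11.3.3.3 keeps only the proportion of subjects receiving IV iron: "This will be performed for week 1 to week 36 as well".

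**Calculation.** SAP 11.2.2.4 gives monthly use as "Total IV iron in mg / [(last visit date – first dose date of study medication +1)/ 28" in square brackets. The otherwise parallel formula in 11.3.3.3 starts its denominator at the "first dose date of study medication in the period". Section 11.2.2.4 has no rule for subjects who stop before Week 28. Section 11.2.2.1 does have one for the hemoglobin responder endpoint: early dropouts count as non-responders.

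**The concern.** IV-iron use is one of the trial's two secondary objectives, and Test 4 is a confirmatory superiority test. A reader of the protocol expects a result for Weeks 1-36, which starts at conversion from the prior ESA. The SAP would give a result for a mostly different period and would not say that the period had changed. The trial is open-label and IV iron is given at the investigator's judgment, so an unexplained change to this test needs a stated reason.

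The second problem is that the new endpoint is not computable as labelled. The name restricts it to Weeks 28-52, but the formula's denominator starts at first dose and ends at last visit. Two programmers could produce different values for the same subject, and the difference would depend on how long the subject was treated.

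**Working it through.** **Plan's own figures.** The documents give no effect size, SD or power for IV iron, so there is nothing to reproduce for this endpoint. The only power figure is at least 99% for the primary hemoglobin test. With 300 per arm, distance to margin 0.75 - 0.30 = 0.45 and SD 1.25, it reproduces as 99.3%, but it has no bearing here.

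**Overlap of the windows.** SAP Appendix 5 puts Week w at Day 7w + 1.
- Weeks 28-52: Days 197-365, so 365 - 197 + 1 = 169 days.
- Shared part, Weeks 28-36: Days 197-253, so 57 days.
- 57/253 = 22.5% of the protocol window and 57/169 = 33.7% of the SAP window. In whole weeks, 9 of 36 are shared (25%).

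**What the formula returns.** Take constant use of 200 mg per 28 days. Three readings are possible:
- A: iron and time both limited to Weeks 28-52.
- B: iron limited to Weeks 28-52, denominator as printed.
- C: neither limited.

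| Subject | A | B | C |
|---|---|---|---|
| Stops at Week 20 (Day 141) | missing | 0 | 200 |
| Last visit Week 52 (Day 365) | 200 | 200 x 169/365 = 92.6 | 200 |
| Last visit Week 156 (Day 1093) | 200 | 200 x 169/1093 = 30.9 | 200 |

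Under B, two subjects with identical use differ threefold (1093/365 = 2.99) only because one was followed longer. Under C everyone has a value, but it is a whole-treatment average. For the Week 20 stopper the printed denominator is 141/28 = 5.04 periods, so the value is missing only under A.

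**Who is exposed to the ambiguity.** By SAP 11.2.2 the superiority test uses the FAS, which needs one dose and one later hemoglobin and so includes early stoppers. SAP 11.3.3.3 counts IV iron only up to the ET/EOT visit. Protocol 4.1.4 follows early stoppers for survival, cardiovascular events and hospital stays, not for iron. Protocol 4.1 also allows treatment to be shortened for subjects enrolled under the amendments, which could leave more of them with little or no time in Weeks 28-52.

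**Possible size under reading A.** The documents give no discontinuation rate. Assuming a constant rate h per year, the share stopping before Week 28 is 1 - exp(-h x 28/52):
- h = 0.2: 10%
- h = 0.3: 15%
- h = 0.4: 19%
- h = 0.5: 24%

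**The case against.** A reader might infer that subjects who stop before Week 28 simply drop out of Test 4. The SAP does not say so. Its printed denominator is defined for every treated subject, so exclusion is one of three readings, and the 10-24% range belongs to that reading alone.

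A reader might also infer that the early iron data are thrown away. They are not. SAP 11.2.2.4 derives monthly use in successive 28-day periods of treatment, 4.3 keeps time to and proportion with an IV-iron requirement, and 11.3.3.3 runs the proportion over Weeks 1-36. What is absent is a summary or test of the monthly amount over that window. Table specifications are in a separate document not available here, so this statement concerns the SAP text.

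Nor do the documents show that the change was driven by data. They do not say when or why it was made, and Weeks 28-52 is also the US primary evaluation period, which is a plausible reason for it. The objective itself names no window, so the later window could be defended as a design choice.

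Finally, it would be wrong to say that Weeks 1-36 gives a fully randomized comparison and Weeks 28-52 does not. Iron counts only to ET/EOT, so both measures depend on time on treatment, and no passage shows that early stoppers differ from stayers.

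All of this stands, and it limits the point. It does not explain the unflagged change or reconcile the label with the formula. When the SAP moved time to exacerbation of hypertension to Weeks 28-52, it kept the Weeks 1-36 version in 4.3. It did not do this for the IV-iron amount.

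**Conclusion.** The point holds on the text. The tested window was moved, the SAP does not highlight or justify the move, and the protocol's endpoint (monthly mg over Weeks 1-36) is neither summarised nor tested. The contradiction between the Weeks 28-52 label and the 11.2.2.4 denominator is also firm. Its size depends on the reading: none for subjects with constant use under C, and under B a 200 mg rate reported as 92.6 or 30.9 mg. The handling of pre-Week-28 stoppers is undefined. The 10-24% range rests on assumed stopping rates and strict windowing. No bias in the treatment difference can be computed, because the documents give no IV-iron effect, variance or discontinuation rate. This should be corrected before the analysis is run.

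**What to change.** **Preferred.** Make Test 4 the protocol endpoint: IV iron (mg) given in Weeks 1-36, divided by the subject's on-treatment days in Weeks 1-36 over 28, with numerator and denominator confined to the same window. Every FAS subject has some exposure in that window. Report Weeks 28-52, computed in the same way, as supportive and outside the fixed sequence.

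**If Weeks 28-52 stays as the tested window.** Flag and justify the change under protocol 9.6, report the Weeks 1-36 amount alongside, limit both parts of the formula to the window, and state how subjects who stop before Week 28 enter the ANCOVA.

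**Cost.** Wording in SAP 4.2, Table 6 and 11.2.2.4. No new data are needed, since concomitant medication is recorded at every visit. There are downsides. Early iron practice is included, the measure remains on-treatment, and very short exposures give unstable rates: one 200 mg dose in a subject treated for 7 days becomes 200/(7/28) = 800 mg per 28 days. The SAP therefore needs a rule for short exposure, such as weighting by exposure, or a sensitivity analysis.

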5.3 Methodology and Conventions

Continuous variables will be presented by descriptive statistics: n, mean, standard deviation, median, minimum, and maximum. Categorical variables will be tabulated by frequency count and percentage. For efficacy endpoints, the standard error and 95% confidence intervals (CI) will be presented as part of the descriptive summaries.

Safety and efficacy data will be summarized and presented by treatment group and time point in summary tables.

Lab results obtained from the central laboratory will be used for all efficacy and safety analyses. Local laboratory values, if collected in the CRF's, will be listed only in data listing. Unless otherwise stated, all statistical tests will be two-sided hypothesis tests performed at the 5% level of significance for main effects and all confidence intervals will be two-sided 95% confidence intervals.

The secondary endpoints will be tested sequentially using the fixed sequence approach for multiplicity adjustments at an alpha level of 0.05. There will be no adjustments for multiple comparisons for other tests.

All analyses will be performed using SAS® Version 9.1.3 or higher.

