11.2.2.5 Time to first RBC Transfusion

Time to the first RBC transfusion during treatment will be analyzed and compared between the 2 treatment groups using the Cox Proportional Hazards model adjusting for baseline Hb, treatment group and stratification factors.

Non-inferiority of roxadustat vs. Epoetin will be declared if the upper bound of the 2-sided 95% confidence interval of the hazard ratio is less than 1.8 and superiority.

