11.2.2.7 Blood pressure increase

- Time to first exacerbation of hypertension During Weeks 28 to 52

Time to first exacerbation during weeks 28 to 52 will be analyzed and compared between the 2 treatment groups using the Cox Proportional Hazards model adjusting for treatment group and stratification factors.

Superiority of roxadustat vs. Epoetin will be declared if the upper bound of the 2-sided 95% confidence interval of the hazard ratio is less than 1.

Subjects will be censored at the time of the last available blood pressure if an exacerbation in blood pressure does not occur.

Sensitivity analysis will be performed on proportion of subjects with increase in blood pressure at any time during the study, defined as an increase from baseline of ≥ 20 mm Hg systolic BP and sBP >170 mmHg or an increase from baseline of ≥ 15 mm Hg diastolic BP and dBP >100 mmHg. Increases from baseline in blood pressure are considered as confirmed by taking the mean of triplicates. The proportion of subjects with increase in blood pressure will be compared between the 2 treatment groups using logistic regression model adjusting for baseline predialysis systolic and diastolic BP as covariates and treatment group and stratification factors as fixed effects.

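### SAP Table 6 and the methods text disagree on Tests 3, 5 and 7: the 0.05 is not secured for superiority claims at Tests 3 and 5, and Test 7 has two success rules

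*SAP*

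**What the plan says.** SAP 11.2.1 tests the secondary endpoints in a fixed order "in order to maintain the overall two-sided type I error of 0.05". The rule for moving on is: "If the claim of superiority or non-inferiority is successful and the test will progress to the next comparison in sequence". SAP 5.3 adds: "The secondary endpoints will be tested sequentially using the fixed sequence approach for multiplicity adjustments at an alpha level of 0.05", and then: "There will be no adjustments for multiple comparisons for other tests".

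Table 6 lists seven tests. Test 3 is non-inferiority, with no margin given. Test 5 is non-inferiority with a hazard-ratio margin of 1.8. Test 7, the last, is "Superiority and Non-inferiority of roxadustat versus EPO with margin of 1.8".

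The methods text differs at each of these:

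- 11.2.2.3 (Test 3) says "Both Non-inferiority of roxadustat vs. Epoetin and superiority will be tested", and sets the margin at -0.75.
- 11.2.2.5 (Test 5) declares non-inferiority if the upper confidence limit "of the hazard ratio is less than 1.8 and superiority". The sentence stops there, with no rule for superiority.
- 11.2.2.7 (Test 7) reads "Superiority of roxadustat vs. Epoetin will be declared if the upper bound of the 2-sided 95% confidence interval of the hazard ratio" is below 1. It contains no non-inferiority rule.

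**The concern.** A fixed sequence protects the overall error because every confirmatory hypothesis has one place in the order, and a failure stops everything after it. At Tests 3 and 5 the methods text brings in superiority hypotheses that have no place in that order. A non-inferiority success is enough to move on, so superiority could be tested at full alpha beside a chain that also continues at full alpha. The sequence does not cover that.

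Test 7 raises a different problem. Both hypotheses are in Table 6, but the methods text recognises only one, so the same result can be read as success or failure.

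What is at stake is which secondary claims count as confirmatory. The study is open-label, and protocol 9.6 wants the SAP settled early to avoid bias. An open list of hypotheses leaves room to choose after results are visible.

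**Working it through.** **1. The two lists side by side**

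| Test | Table 6 | Methods text |
|---|---|---|
| 3 | Non-inferiority, no margin | 11.2.2.3: non-inferiority (-0.75) and superiority |
| 5 | Non-inferiority, HR margin 1.8 | 11.2.2.5: non-inferiority at 1.8, then superiority with no rule |
| 7 | Superiority and non-inferiority, HR margin 1.8 | 11.2.2.7: superiority only (upper limit below 1) |

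**2. The plan's own figure.** In a strict fixed sequence the first true null is tested once at full alpha, and no later false claim is possible unless that one is made. The overall error is therefore at most 0.05 two-sided, or 0.025 in the direction of a claim for roxadustat. A simulation of 1,000,000 runs gave 0.0251 directional. The stated 0.05 is reproduced for the hypotheses listed in Table 6.

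**3. Adding superiority at Tests 3 and 5 as side branches.** Assume that:

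- superiority is truly absent at the branch or branches;
- the first true null left in the main chain comes after Test 5 (Test 6 in the simulation);
- every earlier gate is passed, with non-inferiority power close to 1 at Tests 3 and 5.

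With k true superiority nulls each tested at full alpha on independent endpoints, the error is 1 - (1 - alpha)^k.

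- One branch plus the main chain (k = 2): 1 - 0.975^2 = 0.0494 directional; 1 - 0.95^2 = 0.0975 two-sided.
- Both branches plus the main chain (k = 3): 1 - 0.975^3 = 0.0731 directional; 1 - 0.95^3 = 0.1426 two-sided.

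The documents give no correlation between endpoints, so a range was simulated (directional error, both branches plus the main chain):

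| Assumed correlation | 0 | 0.3 | 0.5 | 0.8 |
|---|---|---|---|---|
| Error | 0.073 | 0.069 | 0.063 | 0.049 |

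The documents also give no size for the raised hs-CRP subgroup and no transfusion event count. The non-inferiority gates were therefore relaxed under assumed values: 75 to 225 subjects per arm at Test 3 (with the SD of 1.25 from SAP 5.1), 60 to 150 events at Test 5, and correlation 0 or 0.3. The directional error was then 0.062 to 0.073.

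**4. Test 7.** The two hypotheses are nested, since a hazard ratio of at least 1.8 is also at least 1. Test 7 is last, so nothing follows it. If non-inferiority is tested first and superiority second, a false superiority claim needs the upper limit to fall below 1 when the true ratio is 1. That has probability 0.025 (simulated 0.0249), so there is no inflation.

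The contradiction shows in an example. With an upper limit of 1.2, 1.2 < 1.8 is a non-inferiority success under Table 6, but 1.2 > 1 is a failure under 11.2.2.7.

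**The case against.** The strongest reply is that Table 6 is the controlled family and it holds 0.05 as listed. On this view, a superiority test that is missing from the table falls under the sentence in 5.3 that leaves other tests unadjusted, and makes no confirmatory claim. This reading is possible, and it is why the excess is conditional. However, the SAP does not say that these tests are among the others. Both appear in 11.2.2 as part of the primary analysis of secondary endpoints, on endpoints that 5.3 puts under the sequence, and neither is labelled nominal.

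A second reply is that superiority at Test 5 rests on an unfinished sentence. That is fair: only Test 3 clearly states a second test. For this reason the one-branch figure is given separately.

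A third reply is that 7.3% is a ceiling, resting on independence and on passing every gate. That is also fair. The SAP states power for the primary endpoint only.

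A reader might go further and infer that superiority hangs outside the sequence at all three tests, or that the stated 0.05 is lost outright. The documents support neither. Test 7 superiority is inside Table 6 and comes last, and the Table 6 hypotheses on their own keep 0.05.

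**Conclusion.** The two parts of the SAP contradict each other on three of the seven tests. Control at two-sided 0.05 is not secured for confirmatory superiority claims at Tests 3 and 5. If such claims are made, the directional error is about 4.9% with one branch and up to 7.3% with both, against 2.5%. With both branches it falls to between 6.9% and 4.9% as the assumed correlation rises from 0.3 to 0.8. If no such claims are made, there is no excess.

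Test 7 adds nothing to the error. Its fault is that an upper limit between 1 and 1.8 has no agreed meaning. In the Ex-US analysis the order also has to be stated, because 11.2.2 assigns non-inferiority to the PPS and superiority to the FAS, so the two answers do not come from one interval.

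**What to change.** - Give each hypothesis its own ordered line in Table 6, and state which result opens the next line.
- Add the -0.75 margin to Test 3.
- Split Test 7 into non-inferiority (upper limit below 1.8) and then superiority (upper limit below 1), naming the analysis set for each in the Ex-US analysis.
- For superiority at Tests 3 and 5, either place it after Test 7 with a complete decision rule (upper limit below 1 for Test 5) or label it nominal. Both choices return the error to 0.05 two-sided. Making superiority the gate at Test 3 would also control it, but the sequence would then stop whenever only non-inferiority is shown.
- Make 11.2.2.3, 11.2.2.5 and 11.2.2.7 match the table.

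The cost is SAP wording. The only loss is that superiority at Tests 3 and 5 comes later in the sequence or becomes descriptive.
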